### **4.3. Measures to minimize/eliminate bias**

#### **4.3.1. Distribution of patients by study sites**

Patients' recruitment at the study sites will be performed on a competitive basis. Recruitment can be re-opened if the Sponsor's audit reveals patients who do not meet the eligibility criteria or patients with major Protocol violations (with no explanation timely provided to the Sponsor).

#### **4.3.2. Procedure of assigning study IDs**

Patients will be randomized, stratified, and assigned IDs according to the internal guidelines of JSC BIOCAD.

Each study site will be assigned a 2-digit identification number. For example, the first site receives ID 01, the second – 02, the third – 03 etc.

After signing the informed consent form, each patient receives a 5-digit screening ID consisting of a 2-digit site ID and a 3-digit subject's ID (continuing numbering in sequence, as patients are enrolled at this site). This information is recorded in the source documents and screening log. For example, in the study site 02, the first patient who has signed the informed consent form will receive the screening ID 02-001.

When all screening procedures are completed, and the investigator decides that the patient meets all the eligibility criteria, the investigator fills out a screening form and/or an eCRF and sends it to the BIOCAD's clinical study project manager via e-mail or [contact] (ext. 116). If JSC BIOCAD confirms the inclusion of this patient, a BIOCAD's representative stratifies and randomizes the patient, assigns him/her a Subject ID, and e-mails a Randomization Form (with the Subject ID and the drug lot number to be used in this patient) to the investigator. The investigator must record the subject's ID and lot in the source documents and the CRF.

The Subject ID consists of 5 digits with 2 digits for the study site and 3 digits for the sequential subject's ID in the study. For example, subject's ID is "01-112", where

"01" is the site ID,

"112" is sequential subject's ID in the study.

Investigators can also use the centralized electronic randomization system. In this case, the investigator e-mails the screening form and/or eCRF, receives a confirmation from BIOCADC regarding inclusion of the patient, and performs stratification and randomization via the electronic randomization system. The Subject ID and the individual drug lot number are generated automatically.

#### 4.3.3. Stratification procedure

In order to make the arms as balanced as possible, patients will be first stratified, and then randomized.

Stratification will be performed by the following:

- Body weight (< 100 kg/100 kg and more),
- Prior experience with monoclonal antibodies for the treatment of psoriasis (MAb-experienced/MAb-naive),
- PASI score (> 20/ $\geq$  20),
- Psoriatic arthritis (yes/no).

**Table 21.** Description of individual strata.

Stratum	Parameters
Stratum 1	

• Body weight below 100 kg

• The patient has never received monoclonal antibodies before

• PASI < 20

• Psoriatic arthritis: no

Stratum 2	

• Body weight below 100 kg

• The patient has never received monoclonal antibodies before

• PASI < 20

• Psoriatic arthritis: yes

Stratum 3	

• Body weight below 100 kg

• The patient has never received monoclonal antibodies before

• PASI <math>\geq</math> 20

• Psoriatic arthritis: no

Stratum	Parameters
Stratum 4	

• Body weight below 100 kg

• The patient has never received monoclonal antibodies before

• PASI <math>\geq</math> 20

• Psoriatic arthritis: yes

Stratum 5	

• Body weight below 100 kg

• The patient has never received monoclonal antibodies before

• PASI < 20

• Psoriatic arthritis: no

Stratum 6	

• Body weight below 100 kg

• The patient has never received monoclonal antibodies before

• PASI < 20

• Psoriatic arthritis: yes

Stratum 7	

• Body weight below 100 kg

• The patient has never received monoclonal antibodies before

• PASI <math>\geq</math> 20

• Psoriatic arthritis: no

Stratum 8	

• Body weight below 100 kg

• The patient has never received monoclonal antibodies before

• PASI <math>\geq</math> 20

• Psoriatic arthritis: yes

Stratum 9	

• Body weight below 100 kg

• The patient has received monoclonal antibodies before

• PASI < 20

• Psoriatic arthritis: no

Stratum 10	

• Body weight below 100 kg

• The patient has received monoclonal antibodies before

• PASI < 20

• Psoriatic arthritis: yes

Stratum 11	

• Body weight below 100 kg

• The patient has received monoclonal antibodies before

• PASI <math>\geq</math> 20

• Psoriatic arthritis: no

Stratum 12	

• Body weight below 100 kg

• The patient has received monoclonal antibodies before

• PASI <math>\geq</math> 20

Stratum	Parameters
	

Psoriatic arthritis: yes

Stratum 13	

Body weight below 100 kg

The patient has received monoclonal antibodies before

PASI < 20

Psoriatic arthritis: no

Stratum 14	

Body weight below 100 kg

The patient has received monoclonal antibodies before

PASI < 20

Psoriatic arthritis: yes

Stratum 15	

Body weight below 100 kg

The patient has received monoclonal antibodies before

PASI <math>\geq</math> 20

Psoriatic arthritis: no

Stratum 16	

Body weight below 100 kg

The patient has received monoclonal antibodies before

PASI <math>\geq</math> 20

Psoriatic arthritis: yes

Stratum 17	

Body weight of 100 kg or more

The patient has never received monoclonal antibodies before

PASI < 20

Psoriatic arthritis: no

Stratum 18	

Body weight of 100 kg or more

The patient has never received monoclonal antibodies before

PASI < 20

Psoriatic arthritis: yes

Stratum 19	

Body weight of 100 kg or more

The patient has never received monoclonal antibodies before

PASI <math>\geq</math> 20

Psoriatic arthritis: no

Stratum 20	

Body weight of 100 kg or more

The patient has never received monoclonal antibodies before

PASI <math>\geq</math> 20

Psoriatic arthritis: yes

Stratum 21	

Body weight of 100 kg or more

The patient has never received monoclonal antibodies before

Stratum	Parameters
	

• PASI < 20

• Psoriatic arthritis: no

Stratum 22	

• Body weight of 100 kg or more

• The patient has never received monoclonal antibodies before

• PASI < 20

• Psoriatic arthritis: yes

Stratum 23	

• Body weight of 100 kg or more

• The patient has never received monoclonal antibodies before

• PASI ≥ 20

• Psoriatic arthritis: no

Stratum 24	

• Body weight of 100 kg or more

• The patient has never received monoclonal antibodies before

• PASI ≥ 20

• Psoriatic arthritis: yes

Stratum 25	

• Body weight of 100 kg or more

• The patient has received monoclonal antibodies before

• PASI < 20

• Psoriatic arthritis: no

Stratum 26	

• Body weight of 100 kg or more

• The patient has received monoclonal antibodies before

• PASI < 20

• Psoriatic arthritis: yes

Stratum 27	

• Body weight of 100 kg or more

• The patient has received monoclonal antibodies before

• PASI ≥ 20

• Psoriatic arthritis: no

Stratum 28	

• Body weight of 100 kg or more

• The patient has received monoclonal antibodies before

• PASI ≥ 20

• Psoriatic arthritis: yes

Stratum 29	

• Body weight of 100 kg or more

• The patient has received monoclonal antibodies before

• PASI < 20

• Psoriatic arthritis: no

Stratum	Parameters
Stratum 30	

• Body weight of 100 kg or more

• The patient has received monoclonal antibodies before

• PASI < 20

• Psoriatic arthritis: yes

Stratum 31	

• Body weight of 100 kg or more

• The patient has received monoclonal antibodies before

• PASI <math>\geq</math> 20

• Psoriatic arthritis: no

Stratum 32	

• Body weight of 100 kg or more

• The patient has received monoclonal antibodies before

• PASI <math>\geq</math> 20

• Psoriatic arthritis: yes

Thus, after stratification, the arms will be balanced by all specified characteristics.

#### 4.3.4. Randomization procedure

Randomization in the study will be centralized. Patients will be randomly assigned to three arms at a 2:2:1 ratio.

Patients included in the study will be randomized within each stratum (block randomization). Thus, after stratification, the arms will be balanced by all specified characteristics.

Block randomization can be described as follows. The random sequence generator generates infinite random sequences consisting of the numbers from 1 to 18 (1,2,3,4,5,6,7,8,9,10,11,12,13,14,15,16,17,18). Each number (1 to 18) corresponds to one of 18 possible unique blocks (see the table below). As the study design does not define in advance the exact number of patients in each of the 32 strata, the patients will be randomized within each stratum to assure the equal distribution between the arms. Therefore, each stratum will contain its own block sequence (symbols “1”, “2”, and “3” corresponding to the 2:2:1 distribution).

Translated from Russian to English, dated 26-Nov-2019

**Table 22.** Examples of blocks for block randomization.

Block	Principle of assigning to treatment arms
#1	1,1,2,2,3
#2	1,2,1,2,3
#3	1,2,2,1,3
#4	1,2,2,3,1
#5	1,2,3,2,1
#6	1,3,2,2,1
#7	3,1,2,2,1
#8	2,2,1,1,3
#9	2,1,2,1,3
#10	2,1,1,2,3
#11	2,1,1,3,2
#12	2,1,3,1,2
#13	2,3,1,1,2
#14	3,1,1,2,2

Block	Principle of assigning to treatment arms
# 15	3,1,2,1,2
#16	3,2,1,1,2
#17	3,2,1,2,1
# 18	3,2,2,1,1

These blocks consist of the following symbols: “1”, “2” and “3”, and each of them corresponds to the study arms, for example, “1” to Arm 1, “2” to Arm 2, “3” to Arm 3.

Finally, a table is generated containing a random block sequence. Each stratum is assigned an infinite random sequence of blocks (an example is shown in 23).

**Table 23.** An example of assigning strata with block sequence.

Stratum	Sequence of blocks
Stratum 1	#1
	6
	5
	2
	...
Stratum 2	4
	3
	5
	#1
	...
Stratum 3	5

Stratum	Sequence of blocks
	5
	#1
	4
	...
...	...

During randomization, the BIOCAD's Clinical Study Manager allocates the patient to an appropriate stratum, assigns him/her the first free arm number in the block and a 3-digit randomization number coding this arm (corresponds to the patient's order number in the study). After randomization, the Clinical Study Manager assigns the patient an investigational product lot number (corresponding to the treatment arm) and a Patient ID. The investigator will know only the subject's ID and investigational product lot number.

For example, the first patient in the study from site #02 is distributed to stratum 2. In this case, he/she receives the first free number of the first block (the first block in this stratum) – 1. Therefore, the patient is distributed to Arm 1 (e.g. the arm treated with BCD-085). After that, the patient is assigned a corresponding 3-digit randomization code (sequential number of the patient in the study), for example, "001" for the first patient, "002" for the second patient, etc. The investigator is notified about the Subject ID (consisting of the site ID and the sequential subject's ID in the study – "02-001") and the lot number of the investigational product that the subject is to receive.

Investigators can also use an electronic centralized randomization system based on the same principles. In this case, the investigator mails the screening form, receives a confirmation from BIOCAD regarding the inclusion of the patient, and performs stratification and randomization via the electronic randomization system. The subject ID and the individual drug lot number are generated automatically. All numbers were automatically generated by the system after the Investigator enters all the required information.

The investigator must record the Subject ID and lot No in the source documents and the eCRF.

JSC BIOCAD should keep the lists of patients' screening, randomization and identification numbers with their randomization arms, lot and batch numbers of the investigational products.

A representative of JSC BIOCADC will monitor the total number of enrolled patients. It is assumed that many patients would fail the screening since the eligibility criteria are rather strict. Therefore, the number of screened patients can be increased depending on the percentage of screening failures.

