 The screening for HBV includes tests for HBsAg and total antibodies to HBcor antigen (anti-HBcor total = IgG + IgM). If the test results for these markers (HBsAg and anti-HBcor total) are negative, the patient is considered eligible for the study by this criterion. If the patient tests positive for HBsAg, the patient cannot be included in the study regardless of the results for anti-HBcor. If the test results for HBsAg are negative but anti-HBcor total antibodies are detected, the patient should undergo an additional examination. The additional examination should include the following: qualitative PCR for HBV DNA, anti-HBcor IgM, and a consultation with the Infectious Disease Specialist. The activity of liver transaminases and concentration of bilirubin in blood chemistry results should be also considered. Having considered the examinations and test results, the Sponsor will decide whether to approve such a patient for the study. If it is known that the patient had hepatitis B infection in the past, an additional examination may be performed along with the main examination (blood samples for HBsAg, anti-HBcor total, anti-HBcor-IgM and blood samples for qualitative PCR to HBV DNA are taken on the same day).

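### In the manual randomization route the sponsor both confirms inclusion and reads the next arm from the block sequence, with no stated separation between the two functions

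*Protocol*

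**What the plan says.** Protocol 4.3.2 and 4.3.4 describe two routes to an assignment.

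**Manual route.** After screening, "the investigator fills out a screening form and/or an eCRF and sends it to the BIOCAD's clinical study project manager via e-mail". Then: "If JSC BIOCAD confirms the inclusion of this patient, a BIOCAD's representative stratifies and randomizes the patient". Section 4.3.4 describes the sequence ("Finally, a table is generated containing a random block sequence", one series of blocks per stratum) and who reads it: "During randomization, the BIOCAD's Clinical Study Manager allocates the patient to an appropriate stratum, assigns him/her the first free arm number in the block". The same person handles supply: "After randomization, the Clinical Study Manager assigns the patient an investigational product lot number (corresponding to the treatment arm) and a Patient ID". The investigator is told only the subject ID and the lot number.

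**Electronic route.** "Investigators can also use an electronic centralized randomization system based on the same principles". The sponsor still confirms inclusion first. The investigator then runs stratification and randomization in the system, which generates the ID and lot number automatically.

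**Discretion at approval.** For a patient with hepatitis B core antibody but no surface antigen, "the Sponsor will decide whether to approve such a patient for the study" (Synopsis, footnote to the exclusion criteria; repeated in 5.2). Sponsor agreement is also needed for patients with hepatitis C antibody, a positive syphilis test or an uncertain tuberculosis test. A footnote in 4.8.2 lets the sponsor accept eligibility violations that the investigator justifies.

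**Blinding.** Section 4.3.5 says that investigators and patients will not know the treatment before Week 12 and does not mention sponsor staff. The sponsor keeps the lists that link patients to arms (4.3.4) and one set of code envelopes (4.10). The SAP (3.1) repeats the stratification factors and the ratio but does not say who holds the list.

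**The concern.** Allocation concealment requires that whoever decides on entry cannot know which arm comes next. In the manual route the decision to include and the reading of the sequence both sit with the sponsor, and nothing in the protocol keeps them apart. A person who can see that the next entry in a stratum is Q4W, Q2W or placebo, and who also has a say in a borderline approval, can let that knowledge influence the decision, knowingly or not.

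The primary conclusion depends on the difference in Week 12 PASI 75 rates between Q4W and Q2W, so selective entry would bias the comparison that matters most. Stratification does not protect against selection on prognosis that the strata do not capture, and the SAP (8.2, 8.6) specifies no covariate adjustment of the primary comparison.

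The exposure may also continue after entry. The sponsor approves early withdrawals (11.3) and longer visit delays (Table 28). If those staff know the arms before Week 12, later decisions in the blinded period are open to the same influence.

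**Working it through.** The point is procedural and the plan gives no figure to reproduce. The check is to set the steps side by side and then ask how much the list holder knows.

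**Step 1: who does what.**

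| Step | Manual route | Electronic route |
|---|---|---|
| Receives screening data | Sponsor's clinical study project manager (4.3.2) | Sponsor (4.3.2, 4.3.4) |
| Confirms inclusion | The sponsor, no role named (4.3.2) | The sponsor, no role named |
| Assigns stratum and arm | Sponsor's Clinical Study Manager, from the block series (4.3.4) | System, run by the investigator |
| Links arm to lot | The same manager (4.3.4) | System, automatically |
| Learns only ID and lot | Investigator | Investigator |

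In the manual route every step before the investigator is informed is a sponsor step. Taking the next unused entry in a block requires sight of that block. No section says that the entry stays hidden until inclusion is recorded. In the electronic route no sponsor sight of the next entry is described.

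**Step 2: how predictable the next arm is.** Inputs: "Patients will be randomly assigned to three arms at a 2:2:1 ratio" and the 18 blocks of five in Table 22.

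- *Sequence in view:* the next arm is known with probability 1.
- *Only the ratio known:* the best guess is Arm 1 or Arm 2, right with probability 2/5 = 40%.
- *Sequence hidden, but the 18 blocks and the earlier arms in the current block known:* for each position, sum the largest matching count over all possible preceding strings and divide by 18. Positions 1 to 5 give 6/18, 11/18, 12/18, 14/18 and 18/18, that is 33%, 61%, 67%, 78% and 100%. The mean is (6+11+12+14+18)/(5×18) = 61/90 = 68%.
- *The same, if all 5!/(2!·2!·1!) = 30 arrangements were used:* 40%, 50%, 53%, 60% and 100%, mean 61%.

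The third line matters for the remedy. Hiding the list while leaving past arms visible would still allow a correct guess about two times in three, so both have to be hidden.

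**Step 3: scale.** In an arm of 85, one patient's outcome is 1/85 = 1.2 percentage points. The documents give no count of discretionary approvals and no split of patients between the routes, so the calculation cannot be carried further.

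**The case against.** The strongest reply has five parts.

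1. *The roles may be different people.* The form goes to a clinical study project manager, inclusion is confirmed by the company, and a Clinical Study Manager draws the arm. A reader might infer that one person does all three. The titles differ and no section says so. The point needs only that all three belong to one organisation with no stated barrier.

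2. *Not every patient is exposed.* A reader might infer that the sponsor sees the coming arm for everyone. The electronic route does not support that. Nor does its existence show that two separate lists are in use: randomization is described as centralized and on common principles. This limits the concern to the manual route.

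3. *Internal guidelines apply.* Section 4.3.2 refers to sponsor guidelines whose content is not given. They may contain a firewall. This stands: only the protocol's silence can be claimed.

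4. *Those who recruit, treat and score PASI remain blinded.* Investigators see an ID and a patient-specific lot in identical cartons (4.3.5). This also stands, so it would be too strong to say that concealment is defeated. The exposure is on the sponsor side.

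5. *Steering is hard.* The sponsor can only approve or refuse, the discretionary cases are narrow, and no link between those markers and PASI 75 is shown. Most of this stands. One qualification: Table 21 as printed lists each combination of the four factors twice (strata 1 and 5 are identical, for example), so the stratum for a given patient is not uniquely fixed. That is a separate defect, but it weakens the claim that the slot is predetermined.

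A reader might also conclude that no analysis could detect or address a problem. The screening logs and retained lists would allow refusals to be checked against the entry that was next in the stratum.

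**Conclusion.** The concern holds for the manual route. The protocol lets the sponsor confirm inclusion, sometimes by judgement, and lets a sponsor employee read the next arm and assign the lot, without stating that the two functions are separated or that sponsor staff are blinded before Week 12. That is a risk of selection bias, and of knowledge of arms during the double-blind period. It is not evidence that either occurred.

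The size can be given only as predictability: certainty for anyone who sees the sequence, against 40% from the ratio alone. A reader might want to turn this into a shift in the response difference and compare it with the non-inferiority margin. The documents do not support that. They give neither the number of affected patients nor their likely response, and the direction of any shift would depend on who was favoured.

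The conclusion assumes that the manual route is actually used and that the unseen guidelines contain no firewall. If either assumption is wrong, a sentence in the protocol would settle the matter. It should be corrected, with medium confidence.

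**What to change.** - Make the electronic central system in 4.3.2 and 4.3.4 the only route, and delete the manual-list text in both sections.
- Require that the inclusion decision is recorded and locked in the system before a lot number is released.
- State in 4.3.5 that the sequence and individual arms are hidden, until the Week 12 unblinding, from the Clinical Study Manager, monitors, the medical expert and anyone who approves inclusion or withdrawal. Name the sponsor function that is unblinded.
- For patients already randomized (4.6.1 of version 2.0 foresees that some may have completed the main period), report how many entered by each route and who had access to the list. Rewording cannot change their allocation.

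The cost is small: protocol wording and access rights in a system already provided for. The drawback is the loss of a manual fallback, which a named unblinded person outside the study team could hold.

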#### **4.3.5. Blinding and subject-specific lots of investigational products**

In the first, blinded, period of the study (until Week 12), neither investigators nor patients will know whether the active drug (BCD-085) or placebo is used.

The investigator (the principal investigator, a member of the study team responsible for the treatment of this patient) will receive BCD-085/placebo in identical secondary packaging (cartons). Each product will have an individual lot number. Each lot number is patient-specific.

Once the patient is enrolled in the study (randomized), the Sponsor will send to the investigator the Subject ID and appropriate lot number of the drug to be given to this patient. If the electronic randomization system is used, all numbers are generated automatically after the investigator enters all the required information. The investigator records the lot numbers in the source documents and the eCRF.

Starting from Week 12 treatment arms will be unblinded. The investigators and patients will be made aware of the drug and the dose used. There will be no individual lots during this study stage. Batch number should be recorded. Unblinding will be performed at Visit 8 (Week 12) by opening the randomization envelopes provided by the Sponsor with the investigational products.

